8.3 Vital Signs Data

Summary statistics for changes from baseline in vital signs and potentially clinically significant results in vital signs will be summarized by parent study (and prior treatment).

Incidence of potentially clinically significant vital sign results will be summarized by parent study (and prior treatment). Criteria of potentially clinically significant vital sign abnormalities are provided in [Appendix 2](#).

8.4 Serum Sodium

The following will be summarized by parent study (and prior treatment):

- Serum sodium excursions above 145, 150, or 155 mmol/L or below 136, 130, or 125 mmol/L

Interruptions of protocol-specified therapies for hypernatremia or hyponatremia.

9 CCI [REDACTED]

[REDACTED]

[REDACTED]

[REDACTED]

[REDACTED]

[REDACTED]

[REDACTED]

[REDACTED]

[REDACTED]

[REDACTED]

9.2 CCI [REDACTED]

[REDACTED]

[REDACTED]

[REDACTED]

Protocol 156-13-211

10

CCI

11 Interim Analysis

There is no interim analysis performed for this trial.

12 Monitoring of Safety Data

For this trial, an Independent Data Monitoring Committee (IDMC), also known as a Data Safety and Monitoring Committee, will be established. The role of the IDMC shall be delineated in a separate IDMC Charter document, but in general this group will meet on a regular basis to ensure the safe and ethical treatment of trial subjects, ensure the scientific integrity of the trial, and to ensure the trial is conducted within the bounds of ethical medical practice. Adjudication results as determined by the HAC will be reported to the IDMC on a quarterly basis or more frequently as necessary. This IDMC may make recommendations to the sponsor and trial steering committee to amend or terminate the trial based on grounds of safety, futility, or greater than expected efficacy as defined by the accepted statistical practices and procedures detailed in their Charter.

13 Changes in the Planned Analyses

None.

Protocol 156-13-211

References

Protocol 156-13-211

Appendices

Appendix 1 Criteria of Potentially Clinically Significant Laboratory Test Abnormalities (Modified NCI Criteria)

(Laboratory Test Abnormalities due to Test Value Increase)

Test	Abnormality	Test Result Grade				
		0	1	2	3	4
APTT (sec)	Increase	ULN	>ULN - 1.5xULN	>1.5xULN - 2xULN	>2xULN	
ALT (SGPT) (IU/L)	Increase	ULN	>ULN - 3xULN	>3xULN - 5xULN	>5xULN - 20xULN	>20xULN
AST (SGOT) (IU/L)	Increase	ULN	>ULN - 3xULN	>3xULN - 5xULN	>5xULN - 20xULN	>20xULN
Bilirubin, Total (mg/dL)	Increase	ULN	>ULN - 2xULN	>2xULN - 3xULN	>3xULN - 10xULN	>10xULN
Creatinine (mg/dL)	Increase Pre-randomization	AB*	>AB - 1.5xAB	>1,5 x AB - 3 x AB	> 3 x AB - 6 x AB	> 6 x AB
Creatinine (mg/dL)	Increase Post-randomization	< 1.33 x PR*	1.33 x PR - < 2x PR	2 x PR - < 3 x PR	3 x PR - 6 x PR	>6xPR
Eosinophils, Absolute (Thous/ μ L)	Increase	≤ 0.65	>0.65-1.5	>1.5-5	>5	
Glucose (mg/dL)	Increase	≤ 115	>115-160	>160-250	>250-500	>500
Hemoglobin (g/dL)	Increase	ULN	>ULN-20	>20-21	>21-22.5	>22.5
Potassium (mEq/L)	Increase	ULN	>ULN-5.5	>5.5-6	>6-7	>7
INR	Increase	ULN	>ULN - 1.5xULN	>1.5xULN - 2xULN	>2xULN	
Sodium (mg/dL)	Increase	≤ 145	146 - 150	151 - 155	156 - 160	>160
Triglycerides (mg/dL)	Increase	ULN	>ULN - 2.5xULN	>2.5xULN - 5xULN	>5xULN - 6xULN	>6xULN
Urea Nitrogen (mg/dL)	Increase	≤ 22	>22-26	>26-31	>31	
White Blood Count (Thous/ μ L)	Increase	≤ 10.799	>10.799-15	>15-20	>20-25	>25

* Baseline creatinine is expected to be elevated in this population. Average baseline (AB) is equal to the mean baseline value collected during screening period.

During treatment with tolvaptan, serum creatinine is expected to increase by approximately 5-10%. When these tables are generated during the double-blind conduct, the post-randomization comparisons will be made to the post-randomization (PR) value which equals the value collected post-randomization at Month 1 visit. After data-base lock, final reporting of unblinded tables and listings, APR should be changed to the highest value obtained during the run-in period matching the subject's assigned treatment, ie, either placebo or tolvaptan run-in periods.

Protocol 156-13-211

(Laboratory Test Abnormalities due to Test Value Decrease)

Test	Abnor- mality	Test Result Grade				
		-4	-3	-2	-1	0
Glucose (mg/dL)	Decrease	<30	30-<40	40-<55	55-<65	≥65
Hemoglobin (g/dL)	Decrease	<6.5	6.5-<8	8-<10	10-<LLN	LLN
Lymphocytes, Absolute (Thous/μL)	Decrease	<0.2	0.2-<0.5	0.5-<0.8	0.8-<LLN	LLN
Neutrophils, Absolute (Thous/μL)	Decrease	<0.5	0.5-<1	1-<1.5	1.5-<LLN	LLN
Platelet Count (Thous/μL)	Decrease	<25	25-<50	50-<75	75-<LLN	LLN
Potassium (mEq/L)	Decrease	<2.5	2.5-<3		3-<LLN	LLN
Sodium (mg/dL)	Decrease	<120	120-124	125-129	130-135	≥136
White Blood Count (Thous/μL)	Decrease	<1	1-<1.5	1.5-<2.5	2.5-<3.501	≥3.501

Protocol 156-13-211

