3.6 Measures to Minimize/Avoid Bias

This is an open-label trial. For subjects entering from placebo-controlled trials, prior therapy (placebo or tolvaptan), will not be known (by trial site, investigator, or sponsor) at the time of entry into this trial.

All blood and urine chemistry will be analyzed and reported by a central laboratory.

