3.7.1 Schedule of Assessments

3.7.1.1 Screening (-30 days to 1 day prior to Baseline)

Screening for eligibility is required for all subjects. The screening and baseline visit may be combined with the last visit from either Trials 156-08-271 or 156-13-210 with all required assessments from each visit performed only once. Therefore, in some cases, if a subject enrolls in this trial from a prior tolvaptan trial, the end of trial or last follow-up visit for that trial and the screening and baseline visit for this one may occur simultaneously. Required assessments for the screening visit are as follows:

1. Obtain subject consent.
2. Obtain subject's new screening identification (ID) assigned by interactive response technology (IRT).
3. Determine subject eligibility through inclusion/exclusion criteria
4. Record demographic information and prior trial identifiers (screening ID, subject ID, site ID, prior tolvaptan ADPKD trial protocol number).
5. Record medical/ADPKD history using prior trial data.
6. Review dietary recommendations and compliance
7. Record vital signs (post-void weight and seated heart rate) and in-clinic calibrated blood pressure (BP) measurement. Record height.
8. Collect blood for serum chemistry, liver function panel (ALT, AST, BT, bilirubin [direct], and alkaline phosphatase), serum sodium, serum creatinine, and hematology and coagulation. Hepatitis testing is optional. If hepatitis testing is performed, then both pre- and post-counseling activities relating to hepatitis testing are to be carried out based on local requirements and best practices.
9. Collect urine for urinalysis, urine osmolality (optional), and urine specific gravity.
10. Perform urine pregnancy test on women of childbearing potential (WOCBP). If positive, a follow-up serum test will be performed.
11. Conduct full physical examination.
12. Enter subject into interactive response technology (IRT) including prior trial identifier/information (protocol number, subject ID), confirmed dose regimen, and scheduled date of next visit.
13. Assess AEs reported as ongoing or resolved from prior trial to determine entry as medical history or ongoing event for this trial.
14. Record ongoing concomitant medications. (This will happen only if the screening visit occurs simultaneously with the last visit from a previous tolvaptan trial).

Protocol 156-13-211

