3.7.1.2 Baseline (Day 0)

The baseline visit is the beginning of the treatment period in this trial. At the baseline visit, subjects will retain the subject number assigned in the previous tolvaptan trial, and the following assessments and procedures will be performed:

1. Review inclusion/exclusion criteria.
2. Review dietary recommendations and compliance.

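### SAP Appendix 1 assigns no valid reference to final on-treatment creatinine grading, because its footnote is written for a randomized, double-blind trial with run-ins

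*SAP*

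**What the plan says.** SAP Appendix 1 gives creatinine two rows. The row labelled pre-randomization grades against AB: "Average baseline (AB) is equal to the mean baseline value collected during screening period". Its grade 1 starts just above 1.0 times AB, and the next cut-offs are 1.5, 3 and 6. The row labelled post-randomization grades against PR, with cut-offs at 1.33, 2, 3 and 6.

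The footnote then gives two instructions. While the trial is running: "When these tables are generated during the double-blind conduct, the post-randomization comparisons will be made to the post-randomization (PR) value", which it equates with the Month 1 value. For the final report: "After data-base lock, final reporting of unblinded tables and listings, APR should be changed to the highest value obtained during the run-in period", taken from whichever run-in (placebo or tolvaptan) matches the assigned treatment. It also says that on tolvaptan "serum creatinine is expected to increase by approximately 5-10" percent.

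The trial described elsewhere is different. SAP 3.1 and 3.2 make it open-label, with tolvaptan for every subject. Protocol 3.7.1.2 states: "The baseline visit is the beginning of the treatment period in this trial". The only blinding is inherited from parent studies: "For subjects entering from placebo-controlled trials, prior therapy (placebo or tolvaptan), will not be known" at entry (Protocol 3.6). SAP 8 sets a general safety baseline, the last value before the first dose in 156-13-211. SAP 11 adds: "There is no interim analysis performed for this trial".

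**The concern.** Long-term safety is the trial's only objective, and the protocol synopsis promises that potentially clinically significant laboratory results will be identified by criteria fixed in advance. For final on-treatment creatinine, the visible criterion cannot be executed as written from this trial's own data: the abbreviation is undefined and the period that it points to is not in the schedule. Whoever programs the tables must supply a reference that the appendix does not name, and the graded counts depend on which one is used.

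**Working it through.** **Step 1. Each visible reference set against the design.**

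| Reference | Computable here? | Assigned to final on-treatment grading? |
|---|---|---|
| APR, highest run-in value | No. It is undefined, and Protocol Table 3.7-1 has no run-in | Yes, by the footnote |
| PR, Month 1 | Yes, for subjects on monthly visits | No. It is limited to tables made in a double-blind phase |
| AB, screening mean | Yes | No. It belongs to the pre-randomization row |
| SAP 8 baseline | Yes | No. It applies in general, and Appendix 1 sets its own creatinine rule |

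The only reference assigned to the final tables is the one that this trial does not generate.

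**Step 2. Month 1 coverage.** Footnote b of Protocol Table 3.7-1 reserves monthly visits for subjects with under 18 months on tolvaptan. Under Protocol 3.7.1.3, subjects from 156-08-271 with more than 18 months of exposure attend every 3 months, so they have no scheduled Month 1 visit. Protocol 3.7.2.2 lists creatinine at monthly visits for all subjects. That fits poorly with the schedule and does not create a Month 1 visit for them.

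**Step 3. What AB amounts to.** The screening draw includes "serum sodium, serum creatinine, and hematology and coagulation" (Protocol 3.7.1.1). No creatinine is scheduled at Day 0, and dosing starts the next day. Unless an extra sample is taken, AB is that single screening value and coincides with the SAP 8 baseline. The pre-randomization row then compares the value with itself: ratio 1.00, grade 0.

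**Step 4. Does the choice matter?** Input: the footnote's expected rise r of 5% to 10%, applied only to subjects off drug at baseline. Let B be the pre-dose value, so the expected Month 1 value is B × (1 + r).

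- Grade 1 under the SAP 8 baseline with the on-treatment cut-offs begins at 1.33 × B.
- Grade 1 under Month 1 begins at 1.33 × 1.05 = 1.3965 to 1.33 × 1.10 = 1.463 times B, about 1.40-1.46.
- The later Month 1 cut-offs become 2.10-2.20, 3.15-3.30 and 6.30-6.60 times B.

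Values from 1.33 B up to the Month 1 cut-off are grade 1 under one reference and grade 0 under the other. Illustration with an assumed B of 1.50 mg/dL: a value of 2.05 is 1.367 × B (grade 1), but 1.302 or 1.242 times the expected Month 1 level (grade 0). A value of 3.0 is 2.0 × B (grade 2), but 1.905 or 1.818 times Month 1 (grade 1).

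**Step 5. Which cut-offs go with a pre-dose reference?** On the AB row, grade 1 covers anything above 1.0 up to 1.5 times AB, so the expected rise alone (1.05 to 1.10) is grade 1. On the on-treatment row it is grade 0. The two rows differ further up as well: 1.2 × B is grade 1 against grade 0, and 1.7 × B is grade 2 against grade 1.

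**Step 6. Price of pairing 1.33/2/3/6 with B.** Relative to the expected on-drug level, an off-drug starter reaches:

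- grade 1 at 1.33/1.10 = 1.209 to 1.33/1.05 = 1.267;
- grade 2 at 2/1.10 = 1.82 to 2/1.05 = 1.90;
- grade 3 at 3/1.10 = 2.73 to 3/1.05 = 2.86;
- grade 4 above 6/1.10 = 5.45 to 6/1.05 = 5.71.

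For a 156-08-271 subject continuing without interruption, B is already on-drug, r is about 0, and the cut-offs stay at 1.33, 2, 3 and 6.

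**The case against.** The strongest defence has four parts.

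First, references exist, and SAP 8 supplies a default baseline. That stands. A reader might infer that creatinine cannot be graded at all, or that a reference must be invented after the data are seen. The documents do not support either inference: three visible references can be computed, and the SAP 8 baseline is a natural fallback. What is missing is a valid assignment of one of them to the final tables.

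Second, text is missing. The supplied SAP jumps from the rules for adverse event dates (SAP 8.1.2) to Hy's Law, Protocol 7.5.2.3 breaks off mid-sentence, and SAP 9 and 10 are redacted. A creatinine rule may sit there. This limits confidence and rules out a flat statement that no subject could be graded. Such a rule would still conflict with the footnote, which would need correcting.

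Third, assigned treatment and unblinding could refer to a parent trial. The reading is not excluded, but the visible text neither describes a parent-trial run-in nor imports a value from one, and it would not obviously cover subjects from open-label 156-08-271.

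Fourth, the absence of an interim analysis does not rule out safety tables for the data monitoring committee while 156-13-210 was still blinded. That is fair, and the point does not rest on it: such tables would not be the final ones.

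A fair criticism also applies to the remedy. Appendix 1 pairs its pre-dose reference with 1/1.5/3/6 and its on-drug reference with 1.33/2/3/6. Using the second set with a pre-dose reference is a new pairing that must be justified and disclosed.

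**Conclusion.** The creatinine rows and footnote are wrong as written for this trial. In the visible text, the final-table reference is undefined and has no counterpart in the schedule. Month 1 is restricted to a phase that this trial does not have and is unscheduled for subjects on 3-monthly visits. No computable reference is validly assigned to final on-treatment grading.

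The size is a shift in where grade 1 begins for off-drug starters, from 1.33 to about 1.40-1.46 times the pre-dose value. It rests on the SAP's own 5-10% figure. It compares two possible choices and does not measure an error in a reported count. Little shift is expected in continuing 156-08-271 subjects.

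A reader might infer that the creatinine safety assessment as a whole is compromised. That goes too far. The trial is descriptive, with no inferential safety analysis. Change-from-baseline summaries (SAP 8) and laboratory changes that investigators judge abnormal, which count as adverse events (SAP 8.1.1), remain as partial cover. Only the graded counts are affected. The point should be fixed; confidence is moderate because of the missing text.

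**What to change.** Remove the randomization, double-blind and run-in/APR wording. Name the SAP 8 baseline, B, as the single reference for all creatinine values after the first dose, and present results by parent study and prior treatment. Use the existing on-treatment cut-offs: grade 0 below 1.33 B; grade 1 from 1.33 B to below 2 B; grade 2 from 2 B to below 3 B; grade 3 from 3 B to 6 B; grade 4 above 6 B. State the reason: the other row's cut-offs would label the expected rise as grade 1.

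Add a footnote that these cut-offs were set for an on-drug reference, so grade 1 begins at about 1.21-1.27 times the expected on-drug level in off-drug starters against 1.33 times in continuing 156-08-271 subjects, and that grades are therefore not directly comparable between those groups. Month 1-referenced grades may be added as supplementary where a Month 1 value exists. Align any creatinine rule in the SAP laboratory section or Protocol 7.5.2.3 with the appendix.

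The cost is appendix wording and one derived reference variable. Screening creatinine is already collected, so no new data are needed.

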Appendix 2 Criteria of Potentially Clinically Significant Vital Sign Abnormalities

Test Type	Test Parameters	Unit	Sex	Criteria (meet either one will count)	
				Limit	Change from baseline
VITAL SIGNS	SBP, SITTING	mmHg	Male/Female	≥ 180	≥ 20
VITAL SIGNS	SBP, SITTING	mmHg	Male/Female	≤ 90	≤ -20
VITAL SIGNS	DBP, SITTING	mmHg	Male/Female	≥ 105	≥ 15
VITAL SIGNS	DBP, SITTING	mmHg	Male/Female	≤ 50	≤ -15
VITAL SIGNS	HEART RATE	bpm	Male/Female	≥ 120	≥ 15
VITAL SIGNS	HEART RATE	bpm	Male/Female	≤ 50	≤ -15
VITAL SIGNS	TEMPERATURE	degree C	Male/Female	≥ 38.3	≥ 1.1
VITAL SIGNS	WEIGHT	kg	Male/Female		≥ 7 percent

This page is a manifestation of an electronically captured signature

SIGNATURE PAGE

Document Name: P15613211_SAP

Document Number: 0001251745

Document Version: 2.0

Signed by	Meaning of Signature	Server Date (dd-MMM- yyyy hh:min) - UTC timezone
PPD	Safety Approval	31-Oct-2018 22:22:05
	Clinical Approval	06-Nov-2018 16:20:29
	Biostatistics Approval	31-Oct-2018 23:59:21
